SECONDARY ENDPOINTS AND OBJECTIVE(S)	
 1. To determine the risk of disease progression, overall and event-free survival, and non-relapse mortality, following treatment with TLI/ATG/TBI 2. To determine the incidence of acute and chronic GVHD following treatment with TLI/ATG/TBI
STUDY OBSERVATION PERIOD	Patients will be followed for 1 year from the time of transplant
TREATMENT SUMMARY	The efficacy of non-myeloablative allogeneic transplantation is mediated in part by the establishment of an alloreactive donor T-cell compartment following transplant with minimal toxicity. The objective of this study is to evaluate whether a single administration of low-dose TBI to standard TLI/ATG non-myeloablative transplant conditioning will help to augment donor chimerism without reducing tolerability of this regimen or increasing the risk of GVHD. This is a single institution, open-label, single treatment study evaluating the efficacy of low-dose TBI added to TLI/ATG in adults with leukemia and lymphoma undergoing allogeneic HCT from sibling or unrelated donors.
SAMPLE SIZE	20 patients
SUMMARY OF SUBJECT ELIGIBILITY	
Patients with the following histologically-confirmed disease:
 
 1. Acute myeloid leukemia (AML) 2. Chronic lymphocytic leukemia (CLL) 3. Myelodysplastic syndrome (MDS) / Myeloproliferative disease syndrome (MPD) 4. Non-Hodgkin lymphoma (NHL) 5. Hodgkin lymphoma (HL) 
Patients not undergoing ablative transplant conditioning
 
Patients with HLA-matched or single antigen/allele mismatched related or unrelated donors.

CONTROL GROUP	Not applicable. Single-arm study.

LIST OF ABBREVIATIONS and DEFINITION OF TERMS

AE	Adverse event	Kg	Kilograms
AML	Acute myeloid leukemia	KPS	Karnofsky performance status
ALT	Aspartate aminotransferase	LVEF	Left ventricular ejection fraction
AST	Alanine aminotransferase	MC	Mixed chimerism
ATG	Anti-thymocyte globulin	MDS	Myelodysplastic syndrome
BID	bis in die (twice-a-day)	MEP	Megakaryocyte erythroid progenitors
CFR	Code of Federal Regulations	MG	Milligrams
cGY	Centigray	MkP	Megakaryocyte progenitors
CLL	Chronic lymphocytic leukemia	MMF	Mycophenolate mofetil
CLP	Common lymphoid progenitors	MPD	Myeloproliferative disease syndrome
CML	Chronic myelogenous leukemia	MPPS	Multipotent progenitors
CMML	Chronic myelomonocytic leukemia	NCI	National Cancer Institute
CMP	Common myeloid progenitors	NHL	Non-Hodgkin lymphoma

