2.5 Reduced Intensity Transplant Conditioning

Following the recognition that a main mechanism of disease control after allogeneic HCT is by donor derived immune mediated GVT reactions, multiple groups, including our own at Stanford, developed reduced intensity transplant conditioning (RIC) regimens that shifted the burden of disease control from high doses of chemoradiotherapy to the donor immune system [23-25]. The low intensity transplant conditioning has allowed older patients and those with medical co-morbidities to proceed with transplant whereas, before these patients were excluded from allogeneic transplantation as the full dose conditioning regimens were associated with prohibitive toxicities. As a consequence of the low-dose conditioning, host hematopoietic and immune cells persist and result in a state of mixed hematopoietic and lymphoid chimerism (MC) that may convert to full donor chimerism (FDC) over a variable time course (13, 28-30). Importantly, the achievement of early (before Day 60) FDC appears to be a necessary precondition for disease control ([26, 27]. We and others have reported that irrespective of the specific type of RIC regimen used, the relapse risk is significantly higher in patients with persistent MC compared to those with FDC, and likely reflects tolerance of donor cells to recipient tissues (13, 28-30). In a report detailing the outcomes of 111 allogeneic HCT recipients from HLA-matched and single

antigen mismatch donors following TLI-ATG conditioning for leukemia and lymphoma there was a very low incidence of severe (Grade 2 to4) acute GVHD (< 5%), and a low incidence of non-relapse related mortality at 1 year (< 5%) (13). Whereas almost all patients who failed to achieve FDC experienced disease relapse, the actuarial event free survival was more than 55% in the patients who achieved > 95% donor type chimerism, with observations extending up to 6 years (13).

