2.7 Study Rationale

The persistence of mixed hematopoietic cell chimerism is associated with a significantly high risk of disease relapse after allogeneic HCT [13, 28-30]. Once the patient's disease has relapsed after allogeneic HCT, the likelihood for long-term survival is poor. Therefore, a strategy that can help promote conversion of mixed to complete hematopoietic cell chimerism prior to disease relapse, and does not promote significant GVHD has the potential to help improve the outcomes of allograft recipients by reducing the risk of disease relapse. The goal of the current proposed trial will be to determine if the addition of very low-dose TBI to standard TLI-ATG conditioning therapy will increase the proportion of patients with FDC at Day 28 post-transplant, without reducing tolerability or increasing transplant morbidity. We **hypothesize** that the addition of very low-dose TBI at 80 cGy to TLI-ATG will result in at least a 30% increase in the proportion of patients with FDC in the CD3 subset at Day 28 post-HCT. This study will follow a single-arm Simon 2-stage trial principle. In Simon stage 1, we will enroll 11 patients, and if 5 or fewer patients respond, defined as $\geq 95\%$ donor chimerism in the CD3 compartment at Day 28, we will stop for futility. If 6 or more respond in Simon stage 1, then in stage 2 we will continue to enroll a full sample of 20 patients and declare success if a total of 11 or more patients respond. The primary endpoint will be the determination of the rate of conversion from mixed to complete donor chimerism. Secondary endpoints will include the risk of acute and chronic GVHD, freedom from disease progression, event-free and overall survival, and the relapse rate. The goal is to improve the rate of attaining complete chimerism without increasing the risk of GVHD. If following the Simon 2-stage trial the results are encouraging, we will expand our experience to a broader trial to determine if the TLI/ATG/low-dose TBI is associated with significantly lower rates of disease relapse.

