7. STUDY CALENDAR

	Pre-enrollment requirements		Day -11, -10, -9, -8, -7	Day -4	Day -3	Day -2	Day -1	Day 0	Day 28 +/- 7 days	Day 56 +/- 14 days	Day 90 +/- 14 days	Day 180 +/- 4 weeks	Day 360 +/- 8 weeks
	Day -180 to -13	Day -42 to -12											
Informed consent	X												
Demographics	X												
Donor evaluation	X												
B-HCG ^a		X											
Height		X											
Weight		X						X	X	X	X		
Medical history	X							X	X	X	X		
Concurrent meds		X						X	X	X	X		
Physical exam	X							X	X	X	X		
Vital signs ^b		X						X	X	X	X		
Performance status	X							X	X	X	X		
Central venous catheter		X											
Blood sample for:		↓						↓	↓	↓	↓	↓	↓
CBC w/diff		X						X	X	X	X		
Serum chemistry ^c		X						X	X	X	X		
STR analysis ^d									X	X	X	X	X
TLI ^e			X	X	X	X	X						
TAC ^f					X								
ATG ^g			X										
TBI ^h							X						
PBSC Infusion								X					
MMF ⁱ								X					
SAE evaluation								X - Weekly from Day 0 through Day 90					
Disease Status Assessment ^j	X									X	X as indicated	X as indicated	

- a: Pregnancy test for women of childbearing potential only.
- b: Temperature, blood pressure, and pulse.
- c: Albumin, alkaline phosphatase, total bilirubin, calcium, chloride, creatinine, glucose, potassium, total protein, AST, ALT, sodium
- e: TLI: Total lymphoid irradiation, 120 cGy.
- f: TAC: Tacrolimus
- g: ATG: Anti thymocyte globulin, 1.5 mg/kg with solumedrol 1.0 mg/kg.
- h: TBI: Total body irradiation, 80 cGy.
- i: MMF: Mycophenolate mofetil, by mouth.
- j: Response assessment as per disease histology, and may include CT, PET, and/or MRI imaging, and bone marrow biopsy or aspiration (refer to Appendix B), and is typically performed around Day 90 post-transplant (Day 0).
- k: Short tandem repeat (STR) analysis (by comparison to subject's pre-study HLA analysis) on Day 28 +/- 7 days; Day 56 +/- 14 days; Day 90 +/- 14 days; Day 180 +/- 4 weeks; Day 360 +/- 4 weeks, and thereafter as per standard of care.

8. MEASUREMENTS and STATISTICAL METHODS

Our extensive experience with the TLI ATG conditioning for allogeneic HCT in cancer patients showed a 30 to 40% incidence of FDC at Day 90, with a 95% confidence interval of 10 to 49%. The non-relapse mortality (NRM) was 3% (95% CI: 0 to 14%) at 100 days and 6% (95% CI: 1 to 28%) at 1 year. The incidence of acute GVHD by Day 100 was 6% (0.7 to 22%).

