8.1 Primary and Secondary Outcome measures

The primary outcome is to determine the proportion of patients with full dose donor chimerism (FDC) at Day 28 following TLI/ATG/TBI conditioning. FDC is defined as achieving $\geq 95\%$ donor type in the CD3+ lineage within 28 days of donor cell infusion.

The secondary outcome measures include time-to-disease progression assessed at 1 year after hematopoietic cell transplantation (HCT); overall survival (OS) at 1 year; and event-free survival (EFS) at 1 year; and non-relapse mortality at 1 year. The incidence of acute and chronic GVHD following the infusion of allogeneic CD8+ memory T-cells will be assessed at 1 year after HCT.

Recipients will be monitored for HCT toxicities and the rates of GVHD as per the study calendar. STR analysis will be performed on Day 28 +/- 7 days and per the study calendar thereafter. The level of tumor burden will be evaluated at 3 months after transplant and at 6 and 12 months as clinically indicated by standard imaging and blood evaluation procedures specific for the patient disease (refer to Appendix B).

Beyond 12 months and per regular medical care for HSC transplant patients, all recipients will be followed long-term and tracked via the Stanford BMT patient database for overall survival; event-free survival; and late complications such as but not limited to relapse; late chronic GVHD; and infections.

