10. STATISTICAL CONSIDERATIONS

10.1 Statistical Analysis

The sample size determination for the clinical trial will follow a single arm Simon 2-stage trial principle. The null hypothesis that the true response is $p_u = 0.40$ will be tested against a one-sided alternative ($p_d = 0.7$). In the first stage, $n_1 = 11$ patients will be accrued. If there are $r = 7$ or fewer responses in these $n_1 = 11$ patients, the study will be stopped. Otherwise, $n - n_1 = 9$ additional patients will be accrued for a total of $n = 20$. The null hypothesis will be rejected if $r + 1 = 11$ or more responses are observed in $n = 20$ patients. This design yields a type I error rate of $\alpha = 0.10$ and power of $1 - \beta = 0.90$ when the true response rate is $p_d = 0.70$.

We plan to use a dose of 80 cGy of TBI on Day -1 of HCT. It is fully expected that this low-dose will be safe and not provoke or increase the risk of GVHD or other complications. Patients will be evaluated for toxicities, defined as new Grade 3 to 4 toxicities, according to the Common Terminology Criteria for Adverse Events (CTCAE) v.5 and Grade 3 to 4 GVHD (Appendix A) during the 90 days following HCT.

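### Success at 11 of 20 supports a Day 28 full-donor-chimerism rate above 40%, not a 30-point gain over TLI/ATG, because no Day 28 TLI/ATG rate is given; the two Stage 1 futility bounds also conflict

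*Combined protocol and SAP*

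**What the plan says.** **Aim.** Section 2.7 (Study Rationale) sets out to learn whether "the addition of very low-dose TBI to standard TLI-ATG conditioning therapy will increase the proportion of patients with FDC at Day 28". It hypothesises "at least a 30% increase in the proportion of patients with FDC in the CD3 subset at Day 28 post-HCT". A move from 0.40 to 0.70 is 30 percentage points, so I read the 30% as absolute; the text does not say.

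**Control.** The Protocol Synopsis entry for a control group is "Not applicable. Single-arm study".

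**Test.** Section 10.1: "The null hypothesis that the true response is $p_u = 0.40$ will be tested against a one-sided alternative ($p_d = 0.7" (closing bracket omitted). It claims a type I error of 0.10, and power of 0.90 when the true rate is 0.70. It gives no citation, dataset or reasoning for 0.40.

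**Endpoint.** Section 8.1 counts a patient as a responder at 95% or more "donor type in the CD3+ lineage within 28 days of donor cell infusion".

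**Past TLI/ATG rate.** Section 8 says earlier experience "showed a 30 to 40% incidence of FDC at Day 90, with a 95% confidence interval of 10 to 49" (percent). That sentence gives no number of patients, cell lineage or donor threshold. Section 2.5 describes a series of 111 TLI/ATG recipients but gives no proportion with full donor chimerism at any day. It also says that low-dose conditioning leaves a mixed state "that may convert to full donor chimerism (FDC) over a variable time course".

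**Stage 1 bound.** Section 2.7 stops for futility at 5 or fewer responders of 11. Section 10.1 stops at 7 or fewer of 11. Both sections require 11 or more of 20 for success.

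**Next step.** Section 2.7: "If following the Simon 2-stage trial the results are encouraging, we will expand our experience to a broader trial".

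**The concern.** In a single-arm trial, a comparative statement is only as good as the benchmark behind the null rate. Here the endpoint is CD3 chimerism at Day 28, while the only past rate is for Day 90 with lineage unstated. By the protocol's own account, chimerism status can change between those days. Nothing ties 0.40 to what TLI/ATG alone achieves at Day 28.

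Two readings of the result are at risk. A success could be described as the hypothesised gain over TLI/ATG, which the test does not examine. A failure could be described as showing that no 30-point gain exists, which is unsafe if the Day 28 baseline is below 40%. Since a broader trial depends on whether results look encouraging, the wording of the conclusion has consequences.

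The conflicting Stage 1 bounds add a second uncertainty: the reader cannot tell which rule, and so which error rates, belong to the reported result.

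**Working it through.** **Inputs.** n1 = 11, n = 20, success at 11 or more (Sections 2.7 and 10.1); p0 = 0.40 and p1 = 0.70 (Section 10.1); futility bound r1 = 5 (Section 2.7) or 7 (Section 10.1). All Day 28 baselines other than 0.40 are my assumptions, because the documents give none.

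**Formula.** P(success | p) = sum over x from r1 + 1 to 11 of P(X1 = x) × P(X2 ≥ 11 − x), with X1 ~ Bin(11, p) and X2 ~ Bin(9, p).

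**Step 1: reproduce the plan with r1 = 5.** Terms for p = 0.40:

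| x | P(X1 = x) | P(X2 ≥ 11 − x) | product |
|---|---|---|---|
| 6 | 0.1471 | 0.2666 | 0.0392 |
| 7 | 0.0701 | 0.5174 | 0.0363 |
| 8 | 0.0234 | 0.7682 | 0.0179 |
| 9 | 0.0052 | 0.9295 | 0.0048 |
| 10 | 0.0007 | 0.9899 | 0.0007 |
| 11 | <0.0001 | 1.0000 | <0.0001 |

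The sum is 0.099. The same sum at p = 0.70 is 0.902. The stated 0.10 and 0.90 are therefore right at those two rates under the 5 of 11 bound.

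**Step 2: the same with r1 = 7.** At p = 0.40 the sum is 0.0235; at p = 0.70 it is 0.568. The chance of stopping at Stage 1 when the true rate is 0.70 is P(X1 ≤ 7) = 0.430, against P(X1 ≤ 5) = 0.078. The bound in Section 10.1 does not give the properties stated in the same paragraph.

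**Step 3: what the result would mean at other Day 28 baselines (r1 = 5).**

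| assumed TLI/ATG Day 28 rate | success with no gain | success with a true 30-point gain |
|---|---|---|
| 30% | 1.3% | 67% (true rate 60%) |
| 35% | 4.0% | 80% (true rate 65%) |
| 40% | 9.9% | 90% (true rate 70%) |
| 45% | 20% | 96% (true rate 75%) |

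**Step 4: does success show 30 points?** Suppose the baseline were known to be 40%. A true rate of 55% (a 15-point gain) succeeds with probability 0.50, and 60% (a 20-point gain) with probability 0.67. The smallest successful result, 11/20, is an observed 55%, which is 55 − 40 = 15 points above the null. Its exact 95% interval is 32% to 77%, treating n = 20 as fixed and ignoring the two stages. If the 30% were meant as relative, the target would be 0.40 × 1.3 = 0.52, where success has probability 0.40.

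**Step 5: direction.** If mixed chimerism converts to full donor chimerism over time, the Day 28 rate is more likely below the Day 90 rate than above it. The value 0.40 equals the top of the Day 90 range, so a Day 28 baseline below 40% is the more likely case. No passage shows it.

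**The case against.** The strongest defence has three parts.

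- **The formal objective is not comparative.** The Synopsis, Section 1.1 and Section 8.1 ask only for a proportion, and the design answers that. This stands. The comparative aim appears in Section 2.7, but there it is stated as the goal and hypothesis of the trial.
- **0.40 is conservative.** If Day 28 rates lie below Day 90 rates, a Day 28 rate shown to exceed 40% would itself point to some increase over TLI/ATG. This largely stands as to direction, and it makes over-claiming of *some* gain the lesser risk. It does not establish a gain of 30 points, it rests on a baseline the documents do not report, and the cost is the lower chance of detecting a real gain.
- **No design powered at 0.70 demonstrates 0.70 when it succeeds.** True. That is a reason to word the conclusion carefully; it is not a fault in the design. No passage says outright that success will be reported as a 30-point gain.

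Stronger readings that a reader might infer are not supported:

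- *That the plan misses its stated 90% power.* Section 10.1 claims that power only at a true rate of 0.70, and under 5 of 11 the claim is correct. It makes no claim about a 30-point gain from other baselines.
- *That false success could plausibly reach 31%.* That is the value at a baseline of 49%, the upper limit of the Day 90 interval, and it would need little or no conversion between Day 28 and Day 90. It is an extreme case.
- *That the size of the past cohort can be worked back from the 10 to 49% interval.* Neither the interval method nor the count is given, so any such figure is guesswork.

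**Conclusion.** The point holds in a limited form. The arithmetic of the design is sound at 0.40 and 0.70 under the rule in Section 2.7. What is missing is any link between 0.40 and the Day 28 rate under TLI/ATG alone. Success supports the statement that the Day 28 rate exceeds 40%, and no more.

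With an assumed baseline of 30% to 35%, false success is 1.3% to 4.0%, but a true 30-point gain is missed in about a third to a fifth of trials (1 − 0.67 = 0.33; 1 − 0.80 = 0.20). A negative result could not then be read as excluding that gain. A baseline of 45% would put false success at 20%; this is the less likely direction.

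The Stage 1 bounds are a plain contradiction that needs no assumption: 5 of 11 gives 0.099 and 0.902, while 7 of 11 gives 0.023 and 0.57.

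The sizes rest on the exact two-stage binomial, on an absolute reading of 30%, and on assumed baselines. Section 6 says that enrolment is complete, so the point concerns reporting; no harm to the conduct of Stage 1 is claimed.

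**What to change.** 1. Word the primary conclusion as: *the proportion with at least 95% donor CD3 at Day 28 exceeds (or was not shown to exceed) 40%, one-sided 10% test*. Give the estimate and its confidence interval, and say whether the interval allows for the two stages. Do not claim an increase over TLI/ATG, or the absence of a 30-point gain, unless a Day 28 benchmark is reported alongside.
2. If a historical Day 28 CD3 rate is added, label it post hoc and give its number of patients and exact interval. Write down the cohort, time-window and lineage rules before comparing. The documents do not say whether such data exist. Leave the decision rule unchanged.
3. Reconcile the Stage 1 bound between Sections 2.7 and 10.1, and report which one was applied. Only 5 of 11 matches the stated error rates. If 7 of 11 was used, the stated alpha and power must be replaced by 0.023 and 0.57.

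**Cost.** Items 1 and 3 are text changes, with no new patients or tests. Item 2 is optional and, if the data exist, takes a database query. Section 6 says that only secondary outcomes remain to be determined, so Day 28 results are probably already known. A benchmark chosen now can be biased, and labelling it does not remove that.

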8.1 Primary and Secondary Outcome measures

The primary outcome is to determine the proportion of patients with full dose donor chimerism (FDC) at Day 28 following TLI/ATG/TBI conditioning. FDC is defined as achieving $\geq 95\%$ donor type in the CD3+ lineage within 28 days of donor cell infusion.

The secondary outcome measures include time-to-disease progression assessed at 1 year after hematopoietic cell transplantation (HCT); overall survival (OS) at 1 year; and event-free survival (EFS) at 1 year; and non-relapse mortality at 1 year. The incidence of acute and chronic GVHD following the infusion of allogeneic CD8+ memory T-cells will be assessed at 1 year after HCT.

Recipients will be monitored for HCT toxicities and the rates of GVHD as per the study calendar. STR analysis will be performed on Day 28 +/- 7 days and per the study calendar thereafter. The level of tumor burden will be evaluated at 3 months after transplant and at 6 and 12 months as clinically indicated by standard imaging and blood evaluation procedures specific for the patient disease (refer to Appendix B).

Beyond 12 months and per regular medical care for HSC transplant patients, all recipients will be followed long-term and tracked via the Stanford BMT patient database for overall survival; event-free survival; and late complications such as but not limited to relapse; late chronic GVHD; and infections.

9. REGULATORY CONSIDERATIONS

This study evaluates an approved therapy (anti-thymocyte globulin, ATG) and an established radiotherapy procedure (low-dose total body irradiation, TBI). The study therapy is considered to not represent an increase in risk over that described in the ATG labeling, and on this basis, is considered to be an IND-exempt investigation.

9.1 Institutional Review of Protocol

The protocol, the informed consent and all forms of participant information related to the study (eg, advertisements used to recruit participants) will be reviewed and approved by the Stanford IRB and Stanford Cancer Center Scientific Review Committee (SRC). Any changes made to the protocol will be submitted as a modification and will be approved by the IRB prior to implementation. The Protocol Director will disseminate the protocol amendment information to all participating investigators.

9.2 Data and Safety Monitoring Plan

The Stanford Cancer Center Data and Safety Monitoring Committee (DSMC) will be the monitoring entity for this study. The DSMC will audit study-related activities to determine whether the study has been conducted in accordance with the protocol, local standard operating procedures, FDA regulations, and Good Clinical Practice (GCP). In addition, the DSMC will regularly review serious adverse events and protocol deviations associated with the research to

ensure the protection of human subjects. Results of the DSMC audit will be communicated to the IRB and the appropriate regulatory authorities at the time of continuing review, or in an expedited fashion, as needed.

9.3 Data Management Plan

The Protocol Director, or his designee, will prepare and maintain adequate and accurate participant case histories with observations and data pertinent to the study. The Stanford BMT data monitoring team along with the study coordinator will collect the information required in the Study calendar of events and maintain records for data analysis. The data will be reviewed by the study PI for accuracy against source document data.

